9.4.3 ANALYSIS OF THE SECONDARY ENDPOINT(S)

Secondary outcomes are HIV and HCV incidence over 12 months. Participants who are HIV antibody positive at baseline will be excluded from the analysis. Participants who are HCV RNA positive at baseline and at 6-months (i.e. chronic infection) will be excluded from the analysis. HCV infection will be operationalized as a positive antibody test following a negative antibody test, or for persons who are AB+ at baseline, a positive HCV RNA test following a negative HCV RNA test. We will conduct a missing data analysis to check for differences between participants with and without test results. If more than 5% of the data are missing we will employ full-information maximum likelihood methods using Mplus.

We will compare incidence rates of HIV and HCV infection between the two intervention conditions among intervention participants, and among network members, with GEE modified Poisson regression to estimate relative risks, adjusted for clustering by recruitment site.⁷⁵ We will estimate the effect of intervention condition, adjusting for covariates including age, education, duration of injection, and length of time in Russia if they are related to the outcome at baseline or if they vary significantly across conditions. The results will be reported as relative risk ratios with 95% confidence intervals, and exact p-values.

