1 PROTOCOL SUMMARY

1.1 SYNOPSIS

Title:	MASLIHAT Intervention for Tajik Male Migrants Who Inject Drugs
Grant Number:	1R01DA050464
Study Description:	
This protocol will test the efficacy of the MASLIHAT peer education HIV prevention intervention for Tajik migrant laborers who inject drugs in the host country, against an attention control. The primary outcomes are self-reported risk behaviors among participants and network members over 12 months following the intervention, including syringe sharing, and sex without condom. Follow-up interviews will be conducted at 3, 6, 9, and 12 months. We will conduct HIV testing at baseline and 12-month follow-up, and HCV testing at baseline and 6- and 12-month follow-up. We expect the MASLIHAT intervention to be associated with greater reduction in injection and sexual risk behavior during follow-up compared with the control condition.

Objectives[*]:	
Primary Objective: Assess the efficacy of the MASLIHAT intervention compared to the TANSIHAT control condition for reducing injection equipment sharing, condomless sex, and heavy alcohol use among intervention participants and among their network members.
 
Secondary Objectives: Assess the efficacy of the MASLIHAT intervention compared to the TANSIHAT control condition for reducing the incidence of HIV and hepatitis C infection among intervention participants and among their network members

Endpoints[*]:	
Primary Endpoint: Reduce the proportion of men sharing syringes or other injection equipment in the past 3 months to 10% or less; reduce the proportion of men engaging in condomless sex in the past 3 months to 10% or less. Reduce the proportion of men engaging in heavy alcohol use in the past 3 months to 10% or less.
 
Secondary Endpoints: Reduce the 12-month incidence of HIV and HCV by 50% compared to the control group.
 
We will enroll a total of 420 male Tajik migrant workers who inject drugs in Moscow, including 140 intervention participants (70 MASLIHAT, 70 control group) and 280 network members recruited by the intervention participants for participation in the assessments.

Phase[*] or Stage:	Phase 2
Description of Sites/Facilities Enrolling Participants:	Participants will be enrolled at PRIZMA Research Center in Moscow, Russia.

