- Autonomous NGO "Scientific and Educational Center "Most v budushee" (Bridge to the future) IRB#1 (00010190) in Russia

(2) Referral for medical or psychological treatment as the result of study participation if needed: The project team works closely with the Tajik Union in Moscow as an NGO that advocates and represents the interests of Tajiks in the Russian diaspora including their legal problems related to drug use or other illegal activities. The Union will arrange referral of services for participants who (if any) experience legal problems related to drug use or undue psychological stress due to their participation in the study. Participants who report recent thoughts of self-harm or suicidal ideation during an interview will be referred to the Union for assistance in accessing mental health services.

(3) HIV/HCV rapid testing will be voluntary and sharing results with the research will be optional.

Participants who receive a positive confirmatory test will be referred to the Tajik Union for assistance in accessing follow-up services in Moscow through the Volunteer Doctors Association or linkage to care in Tajikistan.

(4) Procedures for Research Team Management of AEs, SAEs and Other Study Risks: All research staff and session facilitators will be trained in how to recognize and appropriately respond to both an adverse event (AE) and a serious adverse event (SAE) should one should occur as part of the study. Staff members will be instructed that such events or incidents must be reported immediately to the Moscow site coordinator and documented using a specially prepared project form, and then reported within 24 hours to Drs. [name] and [name]. They, in turn, will inform the NIH funding agency and also the IRBs of the University of Illinois at Chicago (FWA00000083), PRIZMA Research Center (FWA00017140), and the Scientific and Educational Center in Moscow (IRB #00010190). Further action will be taken under the advisory guidance of the three IRBs and NIH. (See also below for further details on actions to be taken with a possible breach of confidentiality.)

(5) At subway stops where on-duty Moscow police are known to stop and check the documents of passengers with non-Slavic (Russian) appearance, group facilitators will accompany intervention participants to and from the station to the PRIZMA office for the group sessions.

(6) Strategies to protect privacy and confidentiality:

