4.4 END-OF-STUDY DEFINITION

A participant is considered to have completed the study if he or she has completed the baseline assessment, at least 4 intervention sessions, and the 6-month and 12-month follow-up assessments, and baseline and 12-month HIV and HCV testing.

The end of the study is defined as completion of the 12-month follow-up assessment and HIV/HCV testing shown in the Schedule of Activities (SoA), **Section 1.3**.

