Peer educator personal development. Measures of peer educator personal development (in addition to knowledge and behavior change) will be administered at baseline and at 12-month follow-up, including self-esteem, self-efficacy, and substance use self-stigma. The 10 items of the Rosenberg Self-Esteem Scale^{70, 71} assess a person's overall evaluation of his or her worthiness as a human being, including subscales of self-competence and self-liking. Items are rated on a 4-point scale from 1 (strongly disagree) to 4 (strongly agree). The New General Self-Efficacy Scale⁷² includes 8 items to measure general self-efficacy (e.g. "I will be able to achieve most of the goals that I set for myself.") rated on a Likert scale from strongly disagree to strongly agree. Internalized stigma of substance use will be assessed with 6 items adapted from a measure of HIV stigma⁷³, rated on a 5-point Likert-type scale, e.g. "I feel ashamed of being a person who uses drugs".

Intervention engagement

Session facilitators will record participant attendance, note homework completion, and rate participant engagement at each session.

HIV/HCV counseling and testing.

Intervention participants and network members will be referred to the Moscow HIV Prevention Center (MHPC) for voluntary HIV/HCV rapid and confirmatory testing and counseling following the baseline interview, and later at the 6-month (HCV) and 12-month (HIV and HCV) follow-up. We chose to not require HIV testing as a condition of study enrollment as its impact on study recruitment and participation are unknown. Participants will be informed that their results will be shared with the research study unless they choose to opt out. We will explain the measures we will employ to maintain the confidentiality of the results.

We will give each participant a card with a code number on which test results will be reported. The testing code number will be separate from the research ID number used to identify interviews, and will

consist of a group number and an individual code. The list matching testing codes with research IDs will be kept in a secure REDCap database separate from locator data and interview data. Participants who object to having their test results linked to their personal interview data will be given the option of blacking out the individual code number, keeping only the group number. This will allow us to track results by intervention group even if the results cannot be linked to individuals.

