For HIV and hepatitis C virus (HCV) outcomes, we computed detectable effects for a one-sided Test for the Difference between Two Poisson Rates in a Cluster-Randomized Design, given our sample with $k=30$ subjects per cluster, coefficient of variation (CV) = 0.50 for the control group and CV=1 for the intervention group, $alpha=0.05$, and $power=0.80$. Assuming a base rate HIV incidence of 10% for the control group, we will have at least 80% power to detect an event rate ratio of 0.11, corresponding to an incidence rate of 1% in the treatment group. For HCV, we must assume that a fair number of the sample will be infected as baseline and therefore excluded from the analysis. Assuming 15 subjects per cluster and HCV base rate incidence of 40%, we will have at least 80% power to detect an event rate ratio of 0.21, corresponding to an incidence rate of 8.6% in the treatment group.

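### The HCV at-risk set depends on the 6-month RNA result, so a man RNA positive at baseline with no 6-month result is not excluded, yet cannot become a case

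*Combined protocol and SAP*

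**What the plan says.** Section 9.4.3 sets the HCV exclusion: "Participants who are HCV RNA positive at baseline and at 6-months (i.e. chronic infection) will be excluded from the analysis". It defines infection as a new positive antibody test after a negative one or, "for persons who are AB+ at baseline, a positive HCV RNA test following a negative HCV RNA test". The HIV rule in the same paragraph uses baseline antibody status only.

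The Synopsis gives three HCV test times: "HCV testing at baseline and 6- and 12-month follow-up". The Schedule of Activities agrees. Under Section 8.1, RNA is tested to confirm a positive rapid antibody test, so a man RNA positive at baseline is also antibody positive at baseline.

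Section 9.2 describes the planned HCV set differently: "For HCV, we must assume that a fair number of the sample will be infected as baseline and therefore excluded from the analysis". It carries no 6-month condition.

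For missing results, Section 9.4.3 plans a comparison of men with and without test results, and then: "If more than 5% of the data are missing we will employ full-information maximum likelihood methods using Mplus". Section 8.1 adds that the project coordinator follows up missing test results.

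**The concern.** An incidence analysis needs a risk set made up of people who could become cases, and in a randomised trial that set should not depend on what happens after allocation. The HCV rule departs from this on both counts. Whether a man infected at baseline is removed depends on his attending a test six months after the intervention. If he does not attend, no sentence removes him and no sequence of results can make him a case.

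Two things are at stake. One is the absolute HCV incidence in each arm, which falls if such men are counted as non-cases. The other is the relative risk, which is distorted only if the retained fraction differs between arms. There is also a mismatch between the set that was powered and the set that would be analysed.

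**Working it through.** **1. Which men are affected.** Take a man antibody and RNA positive at baseline.
- 6-month RNA positive: excluded.
- 6-month RNA negative: kept, and a case if RNA positive at 12 months.
- 6-month result absent: not excluded. Only the 12-month result is left. A positive there has no negative before it, and a negative is not an infection. He cannot be a case.

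**2. Is an absent 6-month result foreseeable?** Yes. Section 2.3.3 says "HIV/HCV rapid testing will be voluntary and sharing results with the research will be optional". Section 8.1 gives men who object to linkage the "option of blacking out the individual code number, keeping only the group number", so a code blacked out on the 6-month card leaves nothing to pair with baseline. The completer definition in Section 4.4 asks for "and baseline and 12-month HIV and HCV testing" but not the 6-month HCV test.

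**3. The plan's own figure.** Inputs from Section 9.2: 15 men per cluster, control rate 0.40, CV 0.50 and 1, one-sided alpha 0.05. Section 6.3 gives 12 sites, so c = 6 per arm. The Hayes-Bennett formula is

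power = Φ( |λ₁ − λ₂|·√(c − 1) / √(λ₁/m + λ₂/m + CV₁²λ₁² + CV₂²λ₂²) − 1.645 ).

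With λ₂ = 0.086: 0.314 × √5 / √(0.02667 + 0.00573 + 0.04000 + 0.00740) = 2.486, and Φ(2.486 − 1.645) = 0.800. The detectable rate is 0.0859, a ratio of 0.215. The plan states 8.6% and 0.21, so its figure reproduces with 15 at risk per cluster.

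**4. Dilution if the unclassifiable men are counted as non-cases.** Section 9.2 uses 30 men per cluster overall and 15 for HCV, so 12 × 30 = 360 men, of whom up to 180 are infected at baseline. Let v be the share of those who are RNA positive and q the share of RNA-positive men without a 6-month result. Neither is in the documents. I take v = 0.7 to 1.0 and q = 0.15. RNA-positive men are treated as persistently so.
- v = 0.7: 180 × 0.7 × 0.15 = 18.9 men retained; at risk 360 − 126 = 234; 18.9 / 252.9 = 7.5%.
- v = 1.0: 180 × 0.15 = 27 men retained; at risk 180; 27 / 207 = 13.0%.

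Control incidence (true value 40%) by RNA-positive men per cluster and q:

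| RNA positive / at risk per cluster | q = 5% | q = 15% | q = 30% |
|---|---|---|---|
| 15 / 15 | 38.1% | 34.8% | 30.8% |
| 5 / 25 | 39.6% | 38.8% | 37.7% |

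For example, 0.40 × 15 / (15 + 15 × 0.15) = 34.8%, and 0.40 × 25 / (25 + 5 × 0.15) = 38.8%.

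**5. Relative risk and power.** If q is equal in both arms, both rates shrink by the same factor k and the denominators grow by 1/k. The ratio stays at 0.215. Every term under the root in step 3 scales by k² and the difference by k, so power stays at 0.800.

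With a true null and 10% missing in control versus 25% in MASLIHAT (assumed), per arm:
- v = 1.0: (90 + 9) / (90 + 22.5) = 99 / 112.5 = 0.88.
- v = 0.7: (117 + 6.3) / (117 + 15.75) = 123.3 / 132.75 = 0.93.

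If control has the higher missingness, the ratios are the inverses, 1.14 and 1.08.

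**The case against.** The strongest reply is that the plan nowhere says these men are scored as non-cases. A man with a positive 12-month RNA and no 6-month result cannot be told apart from one who cleared and was reinfected, so his outcome could be treated as missing, and Section 9.4.3 has a missing-data comparison and a full-information likelihood method. This stands in part: the dilution is conditional, and a reader who infers that the plan commits to it goes beyond the text. But those provisions deal with missing outcomes. They do not decide who is at risk, and neither does the follow-up of missing results.

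A second reply is that the planned comparison is a relative risk, which equal missingness leaves alone. That stands fully. A reader might infer a biased treatment effect or lost power; the documents do not support that, since they give no figure for 6-month test uptake in either arm. Some difference is conceivable, because HIV testing is among the conversation topics measured for diffusion (Section 8.1) and the control programme does not cover HIV (Section 4.2), but its size is unknown.

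Third, 15% missing is not documented. Section 9.2 allows 10% attrition for intervention participants and 15% for network members, and the 360 men are roughly what remains after that (140 × 0.90 + 280 × 0.85 = 364), so q must be read as missed testing among men still followed. Pilot follow-up was complete for peer educators and 95% for network members (Section 2.2), though that was interviews, not voluntary testing.

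Fourth, Section 9.2 is a rounded planning assumption, and the rule in 9.4.3 deliberately keeps men who clear infection. Both are fair. The two sections are not aligned, but it would be too strong to call them flatly contradictory.

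**Conclusion.** The point holds as a defect in how the HCV analysis set is defined. On its literal wording, Section 9.4.3 retains men who cannot become cases, on the basis of a voluntary post-randomisation test, while the HIV rule beside it and the planning assumption in Section 9.2 refer to baseline only.

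The consequence is moderate and conditional. If the men are counted as non-cases, they are 7.5-13% of the denominator under the stated assumptions, and fewer if RNA-positive men are fewer; 15 per cluster is an upper value. Bias in the relative risk needs unequal missingness by arm or a differing share of RNA-positive men at baseline. The 0.88 is the far end of the illustration, since it needs every infected man to be RNA positive as well as a 10% versus 25% split. This is a secondary endpoint, but the rule should be settled before results are seen.

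**What to change.** In Section 9.4.3 and in the formal SAP that Section 9.1 promises:
- Define the at-risk set for the main HCV analysis from baseline results only: antibody negative, or antibody positive and RNA negative.
- Exclude men RNA positive at baseline whatever their 6-month result, and whether or not there is one.
- Analyse men RNA positive at baseline with a documented negative RNA at 6 months as a separate reinfection sensitivity analysis, with follow-up from month 6.
- Reconcile the description in Section 9.2 with this rule.

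The cost is wording only, with no change to visits or tests. The few reinfection events among men who clear infection move from the main analysis to the sensitivity analysis. The change does not help where a blacked-out code prevents linking a man's baseline result to his later ones; those men cannot be classified under either rule, and their number should be reported by arm.

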9.4.4 SAFETY ANALYSES

N/A

9.4.5 BASELINE DESCRIPTIVE STATISTICS

We will compare Intervention groups on sociodemographic characteristics of age, ethnicity, region, education, religion, and duration of time in Moscow. We will compare groups on baseline behaviors including alcohol use, drug use, duration and frequency of injection drug use, network characteristics, and injection risk behaviors. We will compute t-tests for continuous measures and chi-square tests for

categorical measures. We will compare the prevalence of HIV and HCV between groups, and we will use Poisson regression to compute relative risks adjusted for sociodemographic and behavioral variables that differ between groups.

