6.3 MEASURES TO MINIMIZE BIAS: RANDOMIZATION AND BLINDING

The 12 recruitment sites will be pair matched and randomly assigned to a study arm. One of each pair will be assigned to MASLIHAT and the other to the control condition. [name] will create the matched pairs based on site characteristics, and randomization will be determined by the PI using a random number generator. A random number will be generated for each site, and within each matched pair, the site with the smaller number will be assigned to MASLIHAT. To minimize bias during recruitment, site assignments will be masked from project staff engaged in recruitment. The PI will inform the Moscow project coordinator of the site assignment as needed for group scheduling, after the first cohort of participants has been filled for the site. Participants will be informed of their assignment at the time of scheduling the group sessions. [name] will also have access to this information as needed, after recruitment activities are underway. Interviewers will be blinded to site assignment, and the same interview instrument will be used for MASLIHAT and control condition participants. Session facilitators, who may become aware of the recruitment sites from which participants originated, will be instructed during training not to reveal this information to interviewers. Intentional or unintentional breaking of the blind is to be reported to the PI.

The randomization codes will be kept in a password-protected file accessible to the PI, co-investigators, the project coordinator, and the data manager. When preparing data for analysis, the data manager will

blind code recruitment site and study arm. Masking will be removed for reporting interim results to the DSMB.

In addition, we will adopt a position of clinical equipoise. Intervention facilitators and interviewers will be informed that we are testing two different interventions, but neither is assumed to be superior to the other. Facilitators will be assigned to one or the other, while interviewers will be blinded to participant condition. Data collection will be conducted by interviewers who are not involved in intervention delivery. Interviews will be standardized using a computer-assisted instrument, and sensitive sections will be self-administered.

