9.2 SAMPLE SIZE DETERMINATION

We estimated power allowing up to 10% attrition among intervention participants and up to 15% attrition among network members. Power calculations were computed using PASS software and considering effects observed in the pilot study.

We expect to see large reductions in syringe sharing and condomless sex in the MASLIHAT intervention group, and little change in these behaviors in the control group. In the pilot study, syringe sharing decreased from 52% at baseline to 0% at six months, and condomless sex decreased from 35% at baseline to 1% at six months. For binary outcomes, we computed Mixed Models Tests for Two Proportions in a 3-Level Hierarchical Design (Level-3 Randomization), with an intracluster correlation of 0.05 and alpha=.01. We computed power for outcomes ranging from 0.30 to 0.50 for the control group, and 0.05 to 0.15 for the MASLIHAT intervention group, and with 10, 20 or 30 subjects per cluster, representing intervention participants, network members, and the complete sample. We will have at least 80% power to detect predicted changes in condomless sex, and over 90% power to detect predicted changes in syringe sharing. In the larger sample, we will have adequate power to detect effects even if they are not as large as anticipated.

The intervention also targets alcohol use and in the pilot study, days of alcohol use in the past month decreased from 5 to 2, with $b/SE = -6.52$, yielding a Cohen's d effect size of -0.69. We estimated power by computing Mixed Models Tests for the Slope Difference in a 3-Level Hierarchical Design with Fixed Slopes (Level-3 Randomization), with subject $icc=0.30$ and $alpha=0.01$, for a standardized mean difference (SMD) of 0.50 to 0.70, with cluster sizes of 10, 20. and 30. For the intervention participants, we will have at least 80% power to detect a $SMD=0.70$; for network members we will have at least 80% power to detect a $SMD=0.50$, and for the complete sample we will have at least 80% power to detect a $SMD=0.41$.

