9.4 STATISTICAL ANALYSES

9.4.1 GENERAL APPROACH

Descriptive analyses of the study sample will include percentages for categorical variables and means and standard deviations for continuous measures. Chi-square tests and t-tests will be computed to compare study arms on baseline sociodemographic measures. We will compare follow-up between conditions using GEE logistic regression. Results will be reported as odds ratios with 95% confidence intervals and exact p-values for 2-tailed tests.

We will examine the distributions of outcome measures to ascertain whether there is sufficient variability to analyze frequency measures as ordinal. Response categories with a small number of responses will be collapsed for analysis. We will analyze missing data patterns to assess the extent of missing data, and to determine if there is evidence of non-ignorable missingness (i.e. missing not at random, MNAR).

We will conduct repeated measures linear, logistic, and modified Poisson regressions using mixed effects models with random intercepts for subject and recruitment site to test the effect of intervention condition on changes in mediator and outcome variables. In the event of missing data in more than 5% of cases, or unbalanced loss-to-follow-up, analyses will be conducted in Mplus using full-information maximum likelihood methods. We will include the interaction of time and participant type (intervention participant vs. network member) to test for differential effects. Following analysis of the main outcomes we will conduct analyses to explore hypothesized mediation and moderation effects.

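### Section 9.4.5 names plain Poisson regression for baseline HIV and HCV prevalence, with no allowance for the 12 randomised sites and no robust variance, so the precision of these relative risks would be mis-stated

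*Combined protocol and SAP*

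**What the plan says.** Section 6.3 sets the unit of randomisation: "The 12 recruitment sites will be pair matched and randomly assigned to a study arm". The Synopsis gives the sample: "We will enroll a total of 420 male Tajik migrant workers who inject drugs in Moscow".

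Section 9.4.5 compares the arms on HIV and HCV prevalence at baseline and says "we will use Poisson regression to compute relative risks adjusted for sociodemographic and behavioral variables that differ between groups". It mentions no GEE, site effect, robust variance or clustering. The tests beside it are also unclustered; Section 9.4.1 says "Chi-square tests and t-tests will be computed to compare study arms on baseline sociodemographic measures".

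Elsewhere the plan writes site into its models. For HIV and HCV incidence, Section 9.4.3 compares the arms "with GEE modified Poisson regression to estimate relative risks, adjusted for clustering by recruitment site". Sections 9.4.1 and 9.4.2 specify mixed models with a site random intercept, but Section 9.4.1 gives their purpose as "to test the effect of intervention condition on changes in mediator and outcome variables". A baseline prevalence is not a change.

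Section 9.2 also expects sites to differ. Power for the binary behavioural outcomes was computed "with an intracluster correlation of 0.05 and alpha=.01", and power for HIV and HCV incidence used "coefficient of variation (CV) = 0.50 for the control group and CV=1 for the intervention group".

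**The concern.** Men from the same site probably resemble each other in infection status, and each site belongs wholly to one arm. A model that treats 420 men as independent then understates the uncertainty of the between-arm relative risk. A second error works the other way: a Poisson variance is too large for a yes/no outcome, and increasingly so as prevalence rises. The two errors do not cancel in general.

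At stake is how the baseline table is read. Section 9.4.3 removes men who are HIV-positive at baseline, and men with chronic HCV infection, from the incidence analyses, so baseline prevalence is the context for the secondary endpoint. A spurious imbalance could cast unwarranted doubt on the incidence result or offer a false explanation for it. At high HCV prevalence, intervals that are too wide could hide a real imbalance.

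**Working it through.** **1. The plan's own figures.** The documents give no error rate for the baseline comparison. The incidence power in Section 9.2 can be reproduced with the Hayes–Bennett formula, with c = 6 sites per arm and one-sided alpha 0.05:

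c = 1 + (z_α+z_β)² × [(λ0+λ1)/y + CV0²λ0² + CV1²λ1²] / (λ0−λ1)²

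- HIV: λ0 = 0.10, ratio 0.11 so λ1 = 0.011, y = 30. The bracket is 0.00370 + 0.00250 + 0.00012 = 0.00632. Dividing by 0.089² = 0.00792 gives 0.798. Then (z_α+z_β)² = 5/0.798 = 6.27, z_β = 2.503 − 1.645 = 0.858, and power is 80.5%.
- HCV: λ0 = 0.40, λ1 = 0.086, y = 15. The same steps give 80.0%.

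Both agree with the stated 80%. So the plan does allow for between-site variation in these infections when it computes incidence power.

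**2. Inputs for the baseline comparison.**

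- Sites: 12, six per arm (Section 6.3). Men per site: 420/12 = 35 (Synopsis).
- HIV prevalence 13.5% (Tajikistan) and 25.6% (Russia), and HCV prevalence 23% to 67% (Tajikistan), from the Background. These are figures for people who inject drugs, not for this sample.
- ICC 0.05 (Section 9.2), stated for behavioural outcomes. Its use for infection prevalence is an assumption.
- A two-sided 5% level, also an assumption, because Section 9.4.5 states none.
- Number tested per site: not given, and testing is voluntary (Section 8.1), so 18 is shown beside 35.

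**3. Formula.** With n men per arm, a Poisson model takes the variance of the log proportion in each arm as 1/(np). The true variance is (1−p)(1+(m−1)ICC)/(np). So

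R = true/assumed variance = (1−p)(1+(m−1)ICC)

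and a nominal 5% test rejects with probability about 2[1−Φ(1.96/√R)].

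Example: HIV at 13.5%, m = 35, ICC 0.05. The design effect is 1 + 34×0.05 = 2.70, R = 0.865×2.70 = 2.34, and √R = 1.53. The false-positive rate is 2[1−Φ(1.96/1.53)] ≈ 20.0%.

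**4. Results.** Each cell gives R, then the false-positive rate from the formula / from simulation (beta-binomial sites, 100,000 trials for the 35-per-site scenarios, Wald test with Poisson variance).

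| Infection, prevalence | 35 tested, ICC 0.05 | 18 tested, ICC 0.05 | 35 tested, ICC 0.01 |
|---|---|---|---|
| HIV 13.5% | 2.34; 20.0% / 19.3% | 1.60; 12.1% / 11.2% | 1.16; 6.9% / 6.5% |
| HIV 25.6% | 2.01; 16.7% / 16.5% | 1.38; 9.5% / 9.2% | 1.00; 5.0% / 4.9% |
| HCV 23% | 2.08; 17.4% / 17.1% | 1.42; 10.1% / 9.7% | 1.03; 5.4% / 5.3% |
| HCV 67% | 0.89; 3.8% / 3.8% | 0.61; 1.2% / 1.3% | 0.44; 0.3% / 0.3% |

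In the first column, nominal 95% intervals for HIV cover about 81% to 84%.

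**5. Without the borrowed ICC.** If the control-arm CV of 0.50 for incidence is applied to HIV prevalence instead, ICC = CV²p/(1−p) = 0.039 at 13.5% and 0.086 at 25.6%. The formula then gives 16.7% and 25.1%. This is an assumption too. It does not carry over to high HCV prevalence: at 67% it would imply an ICC of 0.51.

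**6. Candidate remedies on the same simulated data.**

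- Robust variance without clustering: about 23% for HIV at 35 per site and ICC 0.05, worse than plain Poisson because it removes only the error that was offsetting clustering.
- Robust variance clustered by site, uncorrected: about 10%.
- The same with a 6/5 variance correction and a t reference on 10 df: about 4.4% to 5.3%.
- A t-test on the 12 site proportions: about 5%.

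The simulations leave out covariate adjustment, pair matching and the grouping of network members under index participants.

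**The case against.** The strongest reply is that the defect is read from silence. Section 9.4.5 does not say that the model is unclustered, the plan's other Poisson models for binary outcomes are all of the modified kind and allow for site, and Section 9.1 promises a formal SAP. Shorthand is possible. But the site adjustment is written out in Section 9.4.3 for the same infections and the neighbouring baseline tests are plain, so an analyst following the text would fit an unclustered model. What stands is that the plan fails to specify clustering, not that it rules it out.

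Three further points also stand. Section 9.4.5 promises relative risks but states no interval or threshold; the 95% and two-tailed wording in Section 9.4.1 follows a sentence on comparing follow-up. The documents give no ICC for HIV or HCV prevalence. And the 17% to 19% figure needs every man tested. The rate is smaller with fewer tested or a smaller ICC, and at 25.6% prevalence with ICC 0.01 the two errors cancel almost exactly (0.744 × 1.34 = 0.997).

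A reader might infer that every reported interval will be too narrow. The HCV rows show otherwise. A reader might also infer that the secondary incidence test is compromised. It is not: Section 9.4.3 has its own site-adjusted method, its covariate list does not include baseline infection prevalence, and no decision rule uses the Section 9.4.5 estimate.

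**Conclusion.** The point holds as a gap in specification with a computable consequence. Taken literally, Section 9.4.5 gives relative risks whose standard errors are mis-sized by √[(1−p)(1+(m−1)ICC)]. For HIV the error is usually towards intervals that are too narrow, and it is large only if sites differ about as much as the plan assumes for behaviour and most men are tested. For HCV the direction depends on prevalence: anti-conservative near 23%, slightly conservative at 67% in the main scenario, and strongly conservative there if the ICC is smaller or fewer men are tested.

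All of these sizes rest on an ICC borrowed from behavioural outcomes, external prevalences and an assumed 5% test. The planned primary and secondary tests are unaffected, so this is a worthwhile minor correction and not a threat to the trial's conclusions.

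**What to change.** In Section 9.4.5, replace the Poisson model with the one already named in Section 9.4.3: modified Poisson with a log link and robust variance, clustered by recruitment site. Add a small-cluster correction and a t reference on about 10 df. The correction matters, because with 12 sites the uncorrected cluster variance still gives a false-positive rate of about 10%. Alternatively, report HIV and HCV prevalence by arm and by site, with the number tested, and make no inferential comparison.

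The cost is one sentence of SAP wording, with no change to design or data collection. HIV intervals will usually be wider; HCV intervals may be narrower if prevalence is high.
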